9.5.4 Pharmacokinetic Analyses

RO7049665 concentration data will be pooled with data from other studies for population PK and PK/PD modeling. The methods and results of that population modeling will be reported separately.

9.5.5 Immunogenicity Analyses

The immunogenicity analyses will include all participants with at least one ADA assessment, irrespective of whether or not the participant receives any treatment ([Shankar et al., 2014](#)).

The numbers and proportions of ADA-positive participants and ADA-negative participants at baseline (baseline prevalence) and after study treatment administration (post-baseline incidence during both the treatment and follow-up periods) will be summarized.

The following definition applies to post-baseline samples:

- Participants are considered to be ADA positive if they are ADA negative at baseline but develop an ADA response following study treatment administration (treatment-induced ADA response), or if they are ADA positive at baseline and the titer of one or more post-baseline samples is greater than the titer of the baseline sample by a scientifically reasonable margin such as 4-fold (treatment-enhanced ADA response).
- Participants are considered to be ADA negative if they are ADA negative at baseline and all post-baseline samples are negative, or if they are ADA positive at baseline but do not have any post-baseline samples with a titer that is greater than the titer of the baseline sample by a scientifically reasonable margin such as 4-fold (treatment unaffected).

The relationship between ADA status and safety, efficacy, PK, and biomarker endpoints will be analyzed and reported descriptively via subgroup analyses.

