Immunogenicity was assessed, and positive results for ADA were observed in approximately 50% of patients of the study. There were no results to date indicating ADAs with neutralizing potential against endogenous IL-2.

No significant abnormalities on vital signs or ECG intervals were reported to date and besides the changes on eosinophils, no significant laboratory safety results have been noted in patients with ulcerative colitis receiving 3.5 mg and 7.5 mg of RO7049665.

Detailed descriptions of the chemistry, pharmacology, PK, efficacy, and safety of RO7049665 are provided in the [Investigator's Brochure RO7049665](#).

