9. STATISTICAL CONSIDERATIONS

9.1 STATISTICAL HYPOTHESES

The hypothesis associated with the primary estimand (see Section 3.1) for this study is that the hazard ratio (HR) for the risk of relapse in the 7.5 mg RO7049665 compared with that of placebo is less than 1. In other words, that 7.5 mg RO7049665 increases the time to relapse following forced tapering of CCS/ \pm NSI therapy in participants with confirmed AIH who have been in stable biochemical remission for at least two years (*or less if according to the local practice*) and on stable AIH treatment for *at least 3 months prior to randomization (and who have not had a dose increase 6 months prior to randomization)*.

Six months after the start of CCS tapering, the relapse rate on placebo is assumed to be 45% (van Gerven 2013). It is estimated that treatment with RO7049665 will reduce the relapse rate to 15%. Under the assumption of exponential times to relapse, these six-month relapse rates imply mean times to relapse of 10.0 months in the placebo arm and 36.9 months in the treatment arm, leading to a reference hazard ratio of 0.272.

The hypotheses formally tested in this study are

$$H_0: HR = 1 \text{ vs } H_1: HR < 1$$

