9.2 SAMPLE SIZE DETERMINATION

The sample size for this study is based on independent pairwise comparisons of each RO7049665 group—i.e., high dose (7.5 mg) and low dose (3.5 mg) with placebo. The total sample size required is obtained by multiplying the appropriate per-group size by three. Methods for the control of the family-wise error rate are described both in this section and in Section 9.3.

The reference treatment effect is 0.272. The study will use an overall one-sided type 1 error rate (significance level) of 2.5%. A power of 90% against the reference treatment effect is required.

There will be one opportunity to stop for success before the end of the study, at 50% information. An O'Brien-Fleming-like alpha-spending rule will preserve the type 1 error rate. The success boundary will be binding.

There will be two opportunities to stop for futility before the end of the study: once at 25% information (i.e., when 25% of the maximum number of events have occurred) and once at 50% information (i.e. when 50% of the maximum number of events have occurred). A Pocock-like beta-spending rule will preserve power of the study. The futility boundary will be non-binding.

If the proportional hazards assumption holds, these assumptions imply that 29.1 events (i.e., 30 events for all practical purposes) in the placebo and 7.5 mg RO7049665 arms combined are required to achieve the desired power and significance levels.

Under the assumption that recruitment to the study will take approximately 19 months, that sites will be activated at uniform rate for six months, after which recruitment will plateau, and that follow-up should continue for at most 6 months after the last patient to enter the study is randomized, then recruitment of 28 participants per arm will generate the required number of events.

Table 9 Summary of the Group Sequential Design

Stage	Interim 1	Interim 2	End of study
Information rate	25%	50%	100%
Efficacy boundary (z-value scale)	∞	2.963	1.969
Futility boundary (z-value scale)	-0.046	0.738	
Number of subjects ^{a,c}	31	47	56
Cumulative number of events ^a	7.3	14.5	29.1
Analysis time ^{b,c}	11.7	16.3	25.0
Cumulative alpha spent	<0.0001	0.0015	0.025
Cumulative power	<0.0001	0.3159	0.9000
One-sided local significance level	N/A	0.0015	0.0245 ^d
Efficacy boundary (t)	N/A	0.211	0.482
Futility boundary (t)	1.035	0.679	
Overall exit probability (under H0)	0.4815	0.3136	
Exit probability for efficacy (under H0)	<0.0001	0.0015	

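### Relating time to relapse to ever-positive ADA status favours those who stay relapse-free, so ADA can look protective unless conversion is very early

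*Combined protocol and SAP*

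**What the plan says.** Section 9.5.5 defines ADA status from post-baseline samples. A participant is positive after any treatment-induced or treatment-enhanced response, and negative only if no post-baseline sample qualifies. Incidence covers both the treatment and follow-up periods, and no time window is set. The section then states: "The relationship between ADA status and safety, efficacy, PK, and biomarker endpoints will be analyzed and reported descriptively via subgroup analyses". Table 10 repeats this.

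On who is included: "The immunogenicity analyses will include all participants with at least one ADA assessment, irrespective of whether or not the participant receives any treatment".

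The efficacy endpoint is days from randomization to relapse (Section 3.1.2). Participants stay on treatment until an event, study closure or withdrawal (Section 4.1). Table 2 schedules ADA samples on Days 1, 8, 15, 57, 71, 78, 85, 113, 141, 169, 197 and 225, continuing until relapse. It adds samples at early termination, at confirmation of relapse and at the follow-up visit 4 weeks after the last dose.

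On ADA frequency in the ongoing repeated-dose study, Section 2.2.2.1 says "positive results for ADA were observed in approximately 50% of patients of the study", without onset times. The same section reports onset by Day 8, but after single doses in healthy volunteers. Section 8.6 allows placebo ADA samples to go unanalysed.

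**The concern.** Ever-positive status is settled only at the end of a participant's observation, and relapse ends that observation. An early relapser has few samples in which to turn positive, while a participant followed for a year or more has many. Comparing time to relapse between these groups uses the future to define the groups (guarantee-time or immortal-time bias). The error runs in one direction, towards ADA looking harmless or helpful.

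This matters because ADA formation is a listed risk in Section 2.3, and about half of participants may become positive. Whether ADA erodes efficacy under repeated dosing is an open question that this analysis is meant to inform. No landmark, time-dependent covariate, fixed ADA window or restriction to the active arms is specified anywhere.

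**Working it through.** **1. Inputs and the plan's own figures.** Section 9.1 gives the six-month relapse rates: "Six months after the start of CCS tapering, the relapse rate on placebo is assumed to be 45"% and, for active drug, "It is estimated that treatment with RO7049665 will reduce the relapse rate to 15"%. With exponential times, rate = −ln(1 − p)/6:

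- placebo: −ln(0.55)/6 = 0.0996 per month, mean 10.04 months (stated 10.0)
- active: −ln(0.85)/6 = 0.0271 per month, mean 36.92 months (stated 36.9)
- ratio: 0.0271/0.0996 = 0.272, matching "The reference treatment effect is 0.272"

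A group sequential calculation at one-sided 2.5% and 90% power, with the spending rules of Section 9.2, gives efficacy bounds 2.963 and 1.969, futility bounds −0.046 and 0.738, and 29.09 events (stated 29.1). The design reproduces. The plan gives no figure for the ADA analysis itself.

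**2. The mechanism on one example.** Assume half of participants can convert, with exponential onset at median 3 months, and a last sample 28 days (0.92 month) after exit.

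- Relapse at month 2: 0.5 × (1 − 2^(−2.92/3)) = 0.5 × 0.49 = 25% classed positive.
- Relapse-free to month 12: 0.5 × (1 − 2^(−12.92/3)) = 0.5 × 0.95 = 47% classed positive.

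ADA has no effect here, yet the positive group is enriched for those who did not relapse early.

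**3. Simulation with true ADA HR = 1.** Relapse follows the plan's two rates. Entry is uniform over 19 months (assumption) with data cut at 25 months, so follow-up is 6 to 25 months. ADA samples follow Table 2, including those at the end of participation and 28 days later. Onset under repeated dosing is not in the documents, so it is varied. Ranges span the active and placebo relapse rates.

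| ADA onset (assumed) | Ever-positive HR | Same, no relapse in first 1.5 months (assumed) |
|---|---|---|
| Within 15 days | about 1.0 | about 1.0 |
| Half can convert, mean 2 months | 0.80–0.83 | 0.89–0.92 |
| Half can convert, median 3 months | 0.65–0.67 | 0.73–0.76 |
| Half can convert, median 6 months | 0.57 | 0.64 |
| All can convert, median 6 months | 0.28–0.35 | 0.32–0.40 |

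The second decimal moves slightly with simulation error and with how the delay is modelled.

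**4. The alternatives in the same simulations.** Time-dependent ADA status gives HR 0.99 to 1.02, and a Day 85 landmark gives 0.98 to 1.02.

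**5. At the trial's size.** With 56 active participants at the active rate, the observed ever-positive HR falls below 1 in 50% of simulated trials for Day 8 onset. It does so in 60% at median onset 1 month and 81% at 3 months (half can convert), and in 99% if all convert at median 6 months.

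**6. Denominator.** One participant in an arm of 28 without a post-baseline sample moves incidence from 14/28 = 50.0% to 14/27 = 51.9%.

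**The case against.** The only onset evidence in the documents is Day 8, and at that timing the bias vanishes. The samples at relapse and follow-up also give relapsers extra chances to be classed positive. Without them the HR for onset within 15 days would be 0.94 and 0.91 (active and placebo rates), and with them it is about 1.0. Participants enter in biochemical remission and taper over weeks, so few may relapse before converting. The analysis is descriptive, names no HR or test by ADA status, and feeds no stopping rule. It is also imprecise. About 19 relapses are expected in 56 active participants, so with an even split SE(log HR) is about 2/√19 = 0.46, a 95% factor of about 2.5 either way. Paired PK samples, Treg counts by visit and PK/PD modelling would separately show a loss of exposure or pharmacodynamic effect.

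Most of this stands as a limit on size. It does not remove the point, because single-dose onset cannot exclude later conversion under dosing every two weeks, and the exposure data do not answer the relapse question.

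Three stronger readings are tempting but unsupported:

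- A reader might infer that ADA will look protective. The documents show no late onset, so the risk is open rather than demonstrated.
- A reader might take loss of exposure through ADA as a named human risk. The listed risk is ADA formation. Exposure loss is a monkey finding (Section 2.2.2), and the volunteers showed no apparent effect on PK.
- A reader might infer that anyone without a post-baseline sample counts as negative. Section 9.5.5 does not address that case.

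**Conclusion.** The concern holds as a flaw in the stated classification, with a size that cannot be fixed from the documents. The bias is negligible if conversion occurs within about two weeks, and becomes material at onset of about 2 months or more. If half of participants can convert, the spurious HR is 0.80 to 0.83 at mean onset 2 months and 0.57 at median 6 months. Values of 0.28 to 0.35 arise only if everyone can convert with median 6 months, which the documents do not indicate. All these figures assume exponential onset beyond the two-week case, uniform entry and ADA independent of relapse. They shrink if no relapse occurs in the first 1.5 months.

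Type 1 error, power and the primary conclusion are not affected. What is at stake is the reading of the ADA subgroup, which could mask a real loss of efficacy. The denominator point is minor. This is a worthwhile clarification rather than a required change.

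**What to change.** In Section 9.5.5 and Table 10, specify that time to relapse by ADA status is analysed within the active arms only. Counting unanalysed placebo participants as negative would confound ADA status with treatment. Then use one of two methods:

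- **Time-dependent ADA status**, with a participant moving to positive at the first qualifying sample before relapse. Samples first positive at relapse confirmation or follow-up do not count backwards.
- **A landmark at Day 85**, an existing ADA visit: status fixed at Day 85, and relapses counted after Day 85 among those still at risk.

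Separately, base post-baseline ADA incidence on treated participants with at least one post-baseline sample.

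The cost is a few sentences and one changed analysis, with no new data. The landmark drops participants who relapse before it. At the active rate this is 1 − exp(−0.0271 × 85/30.44) = 7.3%, or about 4 of 56; at the placebo rate it would be 24%. The landmark also treats conversion after Day 85 as negative, which the time-dependent method avoids.

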9.6 INTERIM ANALYSES

Formal interim analyses form an integral part of the analytical strategy for this study and are defined in Section 9.2. During the conduct of each interim analysis, the study team will remain blind to the results of the interim analysis. The interim analysis will be conducted by the statistician who is a member of the study IMC and independent from the study team and its results reviewed by the IMC as a whole.

It is unlikely that the interim (or final) analyses will be conducted precisely at the information fractions assumed in the sample size calculation. In this case, the stopping boundaries for both success and futility will be adjusted to take account of the actual information fractions at which the interim (and final) analyses were actually conducted while at the same time protecting the overall type 1 and type 2 errors of the study.

A further complication is that the planned timing of each interim analysis depends on the number of relapses observed in the 7.5 mg RO7049665 and placebo groups combined. This is a double-blind, three-arm study, so this number cannot be known without breaking the blind on a regular basis. Therefore, the timing of the interims will be estimated by looking at the number of relapses in the study as a whole, with conduct of the interims and the final analysis when the total number of relapses is expected to be 1.5 times greater than the number of events given in Section 9.2; that is, when 12, 23, and 45 events have been observed in the whole study.

The IMC charter will describe the planned interim analyses in detail.

9.7 SUMMARIES OF CONDUCT OF STUDY

All protocol deviations will be listed. Data for study treatment administration and concomitant medication will be listed. The number of participants who were randomized, discontinued, and completed the study will be summarized and listed.

11. SUPPORTING DOCUMENTATION AND OPERATIONAL CONSIDERATIONS

The following section includes standard appendices such as

- [Appendix 1](#) (Regulatory, Ethical and Study Oversight Considerations),
- [Appendix 2](#) (AE: Definitions, Reporting, Procedures for Evaluating, Follow-up, and Reporting)
- [Appendix 3](#) (Procedures of Recording Adverse Events),
- [Appendix 4](#) (Clinical Laboratory Tests),
- [Appendix 5](#) (Contraceptive Guidance and Collection of Pregnancy Information).
- [Appendix 6](#) (Patient-Reported Outcome [PRO] Assessments)

Appendix 1

Regulatory, Ethical, and Study Oversight Considerations

1. REGULATORY AND ETHICAL CONSIDERATIONS

1.1. COMPLIANCE WITH LAWS AND REGULATIONS

This study will be conducted in full conformance with the ICH E6 guideline for Good Clinical Practice and the principles of the Declaration of Helsinki, or the laws and regulations of the country in which the research is conducted, whichever affords the greater protection to the individual. The study will comply with the requirements of the ICH E2A guideline (Clinical Safety Data Management: Definitions and Standards for Expedited Reporting). Studies conducted in the United States or under a U.S. Investigational New Drug (IND) application will comply with U.S. FDA regulations and applicable local, state, and federal laws. Studies conducted in the EU/EEA will comply with the EU Clinical Trial Directive (2001/20/EC).

1.2. INSTITUTIONAL REVIEW BOARD OR ETHICS COMMITTEE

This protocol, the ICFs, any information to be given to the participant (e.g. advertisements, diaries etc), and relevant supporting information must be submitted to the IRB/EC by the Principal Investigator and reviewed and approved by the IRB/EC before the study is initiated. In addition, any participant recruitment materials must be approved by the IRB/EC.

The Principal Investigator is responsible for providing written summaries of the status of the study to the IRB/EC annually or more frequently in accordance with the requirements, policies, and procedures established by the IRB/EC. Investigators are also responsible for promptly informing the IRB/EC of any protocol amendments (Section 2.3.1 of this Appendix).

The Investigator should follow the requirements for reporting all S to the Sponsor. Investigators may receive written IND safety reports or other safety-related communications from the Sponsor. Investigators are responsible for ensuring that such reports are reviewed and processed in accordance with Health Authority requirements and the policies and procedures established by their IRB/EC, and archived in the site's study file.

1.3. INFORMED CONSENT

The Sponsor's Master Informed Consent Form (and ancillary sample ICFs such as a Child's Assent or Caregiver's Informed Consent Form, if applicable) will be provided to each site. If applicable, it will be provided in a certified translation of the local language. Participants must be informed that their participation is voluntary. Participants will be required to sign a statement of informed consent that meets the requirements of 21 CFR 50, local regulations, ICH guidelines, Health Insurance Portability and Accountability Act (HIPAA) requirements, where applicable, and the IRB/IEC or study center. The Sponsor

or its designee must review and approve any proposed deviations from the Sponsor's sample ICFs or any alternate consent forms proposed by the site (collectively, the "Consent Forms") before IRB/EC submission. The final IRB/EC-approved Consent Forms must be provided to the Sponsor for Health Authority submission purposes according to local requirements. Participants must be re-consented to the most current version of the ICF(s) during their participation in the study. A copy of the ICF(s) signed by all parties must be provided to the participant.

The ICFs must be signed and dated by the participant before his or her participation in the study. The case history or clinical records for each participant shall document the informed consent process and that written informed consent was obtained prior to participation in the study.

The ICFs should be revised whenever there are changes to study procedures or when new information becomes available that may affect the willingness of the participant to take part. The final revised IRB/EC-approved ICFs must be provided to the Sponsor for Health Authority submission purposes if required as per local regulations.

If the ICFs are revised (through an amendment or an addendum) while a participant is participating in the study, the participant may be re-consented by signing the most current version of the ICFs or the addendum, in accordance with applicable laws and IRB/EC policy. For any updated or revised ICFs, the case history or clinical records for each participant shall document the informed consent process and that written informed consent was obtained using the updated/revised ICFs for continued participation in the study. The study team will provide guidance for which participants need to re-consent in the event of an update to the ICF.

A copy of each signed ICF must be provided to the participant. All signed and dated ICFs must remain in each participant's study file or in the site file and must be available for verification by study monitors at any time.

Participants who are re-screened are required to sign a new ICF.

Consent to Participate in the Research Biosample Repository

The ICF will contain a separate section that addresses participation in the RBR. The Investigator or authorized designee will explain to each participant the objectives, methods, and potential hazards of participation in the RBR. Participants will be told that they are free to refuse to participate and may withdraw their samples at any time and for any reason during the storage period. A separate, specific signature will be required to document a participant's agreement to provide optional RBR samples. Participants who decline to participate will not provide a separate signature.

The Investigator should document whether or not the participant has given consent to participate by completing the RBR Sample Informed Consent eCRF.

In the event of death or loss of competence of a participant who is participating in the research, the participant's samples and data will continue to be used as part of the RBR.

Approval by the Institutional Review Board or Ethics Committee

Collection, storage, and analysis of RBR samples is contingent upon the review and approval of the exploratory research and the RBR portion of the ICF by each site's IRB/EC and, if applicable, an appropriate regulatory body. If a site has not been granted approval for RBR sampling, this section of the protocol will not be applicable at that site

Withdrawal from the Research Biosample Repository

Participants who give consent to provide samples for the RBR have the right to withdraw their samples at any time for any reason. If a participant wishes to withdraw consent to the testing of his or her samples, the Investigator must inform the Medical Monitor and Site Monitor in writing of the participant's wishes using the RBR Withdrawal Form and, if the study is ongoing, must enter the date of withdrawal on the RBR Withdrawal of Informed Consent eCRF. The participant will be provided with instructions on how to withdraw consent after the study is closed. A participant's withdrawal from Study BP42698 does not, by itself, constitute withdrawal of samples from the RBR. Likewise, a participant's withdrawal from the RBR does not constitute withdrawal from Study BP42698. Data already generated before time of withdrawal of consent to RBR will still be used.

